8.2.3.7 Frequentist analysis – NRI

An estimate of the treatment differences (BKZ versus PBO and BKZ versus ADA) at Week 12 will be obtained from a longitudinal generalized estimating equation (GEE) model for a binary outcome, controlling for Baseline Hurley Stage and including treatment, visit and a treatment by visit (week) interaction term. An unstructured covariance matrix will be used for this analysis. In the event that the model does not converge, alternate covariance structures will be considered.

For subjects who withdraw from the study, any missing responses from visits after the withdrawal will be imputed as non-response. For any missing response data at any visit that is not due to a withdrawal, the response will not be imputed and the GEE model will analyze these as “missing at random”.

At each visit, the number and percentage of responders in each treatment group, together with the estimated treatment differences (odds ratios [BKZ versus PBO and BKZ versus ADA]), will be reported, including 95% CI for the odds ratios.

8.2.3.8 Observed case frequentist analysis

The same model as in [Section 8.2.3.7](#) will be applied to analyze the data. Missing data will not be handled using NRI (ie, observed cases analysis).

The results of the analysis will be presented as described for the analysis in [Section 8.2.3.7](#).

8.2.3.9 Concomitant antibiotic use – Frequentist analysis

An estimate of the treatment differences (BKZ versus PBO and BKZ versus ADA) at Week 12 will be obtained from a longitudinal GEE model for a binary outcome, controlling for Baseline Hurley Stage and including concomitant antibiotic use at study entry (coded as a binary [yes/no] variable), treatment, visit, treatment by visit (week) interaction term and antibiotic use by Baseline Hurley Stage interaction terms. Missing response data will not be handled using NRI (ie, observed cases analysis).

An unstructured covariance matrix will be used for this analysis. In the event that the model does not converge, alternate covariance structures will be considered.

The results of the analysis will be presented as for the analysis in [Section 8.2.3.7](#).

8.2.3.10 Rescue therapy – Frequentist analysis

Subjects who receive specific rescue medication will be considered as non-responders from the point of receiving the rescue medication and the model and presentation of data as specified in [Section 8.2.3.7](#) will be applied. Missing response data will not be handled using NRI (ie, observed cases analysis).

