15.10 Handling of dropouts or missing data

For the analysis of the primary efficacy variable, non-responder imputation will be used to impute missing data for subjects who have missing data at a specific visit and for subjects who discontinue early from the study during the Treatment Period for any reason. These subjects will be defined as non-responders at all subsequent visits after the time of study discontinuation. In additional sensitivity analyses, subjects who receive specific rescue therapy may also be considered a non-responder from the time that the rescue therapy was taken to the end of the Treatment Period.

Further details on all methods to be used for missing data imputation in the analysis of the efficacy variables will be included in the SAP.

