4.2 Handling of dropouts or missing data

4.2.1 Efficacy data

There will be no imputation of missing data for the individual components of the HiSCR (abscess count, inflammatory nodule count and draining tunnel (fistula/sinus tract) count).

For subjects with a missing HiSCR due to missing component data at a specific visit, or due to early discontinuation from the study during the Treatment Period, non-responder imputation

(NRI) will be used for the primary analysis of the primary efficacy variable. These subjects will be defined as non-responders at a specific visit or at all subsequent visits after the time of study discontinuation. In additional sensitivity analyses, an ‘observed cases’ analysis will also be performed (no imputation of missing HiSCR) and subjects who receive specific rescue therapy will also be considered a non-responder from the time that the rescue therapy was taken to the end of the Treatment Period ([Section 8.2.3](#)).

For the hsCRP data, measurements that are below the limit of quantification (BLQ) will be imputed with half of the lower limit of quantification (LLOQ) for the purpose of calculating summary statistics, changes from Baseline and ratio to Baseline.

The handling of any missing data for the other exploratory efficacy data is described or referenced in the respective sections where the analysis of this data is described.

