8.2.3.6 Rescue therapy – Bayesian analysis

The primary Bayesian analysis of HiSCR at Week 12 will be performed and reported as specified in [Section 8.2.2.4](#) and will treat subjects who receive specific rescue medication prior to the Week 12 visit as non-responders, from the point of receiving the rescue medication.

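### The Bayesian and frequentist rescue sensitivity analyses in the SAP use different endpoints: only the Bayesian one also counts withdrawal as failure

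*SAP*

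**What the plan says.** Protocol 15.10 sets the base rule for the primary variable: "non-responder imputation will be used to impute missing data for subjects who have missing data at a specific visit", and likewise for subjects who discontinue early. It then adds, for sensitivity analyses, that "subjects who receive specific rescue therapy may also be considered a non-responder", and leaves further detail to the SAP.

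SAP 4.2.1 uses NRI for the primary analysis. It then names two sensitivity approaches in one sentence: an observed-cases analysis, and one in which "subjects who receive specific rescue therapy will also be considered a non-responder from the time that the rescue therapy was taken", up to the end of the Treatment Period. It does not say whether the rescue approach keeps NRI.

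The detail is in SAP 8.2.3:

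- 8.2.3.6 (Bayesian rescue) runs the primary Bayesian analysis as set out in 8.2.2.4, with one added rule: it "will treat subjects who receive specific rescue medication prior to the Week 12 visit as non-responders, from the point of receiving the rescue medication". Section 8.2.2.4 sends missing data to 4.2.1, so NRI applies.
- 8.2.3.7 (frequentist, NRI) fits a longitudinal GEE. "For subjects who withdraw from the study, any missing responses from visits after the withdrawal will be imputed as non-response". Gaps not caused by withdrawal are left unimputed.
- 8.2.3.10 (frequentist rescue) applies the 8.2.3.7 model, makes subjects non-responders from the point of rescue, and then states: "Missing response data will not be handled using NRI (ie, observed cases analysis".

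The antibiotic pair has the same split. Section 8.2.3.5 repeats the primary Bayesian analysis with extra covariates, while 8.2.3.9 is observed-case.

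**The concern.** A rescue sensitivity analysis asks whether the treatment effect holds up when rescued subjects are not allowed to count as responders. It is easiest to read when rescue is the only thing changed. In 8.2.3.10 two rules change at once relative to its parent, 8.2.3.7: rescue becomes failure, and withdrawal stops being failure. These changes can push the estimate in opposite directions, so a shift between the two results cannot be assigned to rescue.

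If withdrawal is related to lack of response and differs by arm, leaving those visits missing can bias the estimate in the one frequentist analysis that scores rescue as failure. The Bayesian counterpart does not have this gap. If 8.2.3.6 and 8.2.3.10 disagree, part of the disagreement may come from the endpoint and not from the method.

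**Working it through.** **Step 1. Set the rules side by side (Week 12 HiSCR).**

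| SAP section | Rescued before Week 12 | Withdrew without rescue, Week 12 not attended | Week 12 missing, no withdrawal or rescue |
|---|---|---|---|
| 8.2.2 primary Bayesian | as observed | failure | failure |
| 8.2.3.6 Bayesian rescue | failure | failure | failure |
| 8.2.3.7 GEE, NRI | as observed | failure | missing |
| 8.2.3.8 GEE, observed cases | as observed | missing | missing |
| 8.2.3.9 GEE, antibiotic | as observed | missing | missing |
| 8.2.3.10 GEE, rescue | failure | missing | missing |

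Here, as observed means that rescue itself does not alter the score. Among the four GEE rows, none has failure in both of the first two columns. Row 8.2.3.10 differs from 8.2.3.7 in two columns and from 8.2.3.8 in one.

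**Step 2. Inputs.** From SAP 2.4: Week 12 HiSCR rates of 70% (bimekizumab) and 27.6% (placebo), with 40 and 20 subjects. The plan gives no figure for this point itself. As a check on the inputs, the probability of success that SAP 2.4 puts at 99% was recomputed by exact enumeration, with Beta(5.52, 14.48) for placebo, Beta(0.5, 0.5) standing in for the vague bimekizumab prior, and no Hurley term. The result is 98.9%, in agreement.

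Assumptions, not in the documents: the share *d* missing at Week 12 after withdrawal without rescue, taken from 5% to 30%; and that 70% and 27.6% are the rates among subjects with a Week 12 score, with rescue already counted as failure.

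**Step 3. Formula.** Rate with withdrawals as failure = observed-case rate × (1 − *d*). Crude odds ratio (OR) = [p1/(1 − p1)] / [p2/(1 − p2)].

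**Step 4. Results.** Observed cases: 70.0 − 27.6 = 42.4 points, OR 6.12, whatever *d* is.

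| *d* bimekizumab / placebo | Rates with withdrawals as failure | Difference | OR | Change from 42.4 |
|---|---|---|---|---|
| 5% / 5% | 66.5% vs 26.2% | 40.3 | 5.59 | −2.1 |
| 10% / 10% | 63.0% vs 24.8% | 38.2 | 5.15 | −4.2 |
| 20% / 20% | 56.0% vs 22.1% | 33.9 | 4.49 | −8.5 |
| 20% / 5% | 56.0% vs 26.2% | 29.8 | 3.58 | −12.6 |
| 5% / 30% | 66.5% vs 19.3% | 47.2 | 8.29 | +4.8 |

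Example (row 4): 0.70 × 0.80 = 0.560; 0.276 × 0.95 = 0.262; 0.560 − 0.262 = 0.298.

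With equal withdrawal the observed-case difference is always the larger, because the other is that difference multiplied by (1 − *d*). With unequal withdrawal either can be larger.

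**The case against.** The best defence is that 8.2.3.10 is deliberate. The no-NRI statement is explicit and appears in similar words in 8.2.3.8, 8.2.3.9 and 8.2.3.10. Section 8.2.3.10 borrows only the model and presentation from 8.2.3.7, so its natural comparator could be 8.2.3.8: same model, same observed-case handling, only the rescue rule changed. That comparison is clean, and this part of the defence stands. The text should not be called a slip. But the SAP nowhere says that 8.2.3.10 is to be read against 8.2.3.8, and the empty cell remains: no frequentist analysis counts both routes of failure.

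It is also fair that the Bayesian and frequentist analyses were never a matched pair. One is a Week 12 model with informative priors reporting rate differences; the other is a longitudinal GEE reporting odds ratios. Even the base pair differs on gaps not due to withdrawal. Aligning withdrawal removes one avoidable difference, not all of them.

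Three stronger readings are tempting and are not supported:

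- A reader might infer that the SAP contradicts the protocol. Protocol 15.10 is permissive ("In additional sensitivity analyses, subjects who receive specific rescue therapy may also be considered a non-responder") and defers to the SAP, so the mismatch lies within the SAP.
- A reader might infer that a subject rescued and then withdrawn has two contradictory scores. Sections 4.2.1 and 8.2.3.10 settle this: the subject is a non-responder from rescue to the end of the Treatment Period, so no missing response is left for the observed-case rule to act on.
- A reader might infer that subjects who withdraw drop out of 8.2.3.10 altogether. Their visits before withdrawal stay in the GEE, and SAP 4.4 asks withdrawn subjects to return for Week 12. Those who attend are scored.

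**Conclusion.** The point holds as an inconsistency within the SAP. The two rescue analyses score the same subject differently at Week 12 when that subject withdraws without rescue and does not attend, and the frequentist set has no analysis in which rescue and withdrawal are both failures.

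The figures are crude Week 12 rates, not Hurley-adjusted GEE estimates, and every withdrawal share is assumed. They show that the choice could matter by a few points, or more if withdrawal is high or uneven; they do not predict its effect in this trial. In every scenario shown bimekizumab stays ahead by at least 29.8 points.

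A reader might infer that the study conclusion is at risk. It is not: proof of concept rests on the primary Bayesian model alone, which uses NRI. In addition, SAP 8.2.5 tabulates HiSCR by rescue use under both NRI and observed cases. This is a cheap improvement to a supportive analysis.

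**What to change.** In SAP 8.2.3.10, replace the observed-cases sentence with a statement that missing responses after withdrawal are imputed as non-response as in 8.2.3.7, and that subjects are non-responders from the time of rescue to the end of the Treatment Period. The comparison with 8.2.3.7 then isolates rescue, and the endpoint comes close to that of 8.2.3.6, differing only for gaps not due to withdrawal or rescue. Apply the same 8.2.3.7 missing-data rule in 8.2.3.9.

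Imputing every missing Week 12 value as non-response would match 8.2.3.6 more closely, but neither 8.2.3.7 nor 8.2.3.8, so the clean frequentist comparison would be lost.

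Cost: one sentence in each of two sections, and the same model code with a different input flag. The downside is that the observed-case rescue comparison against 8.2.3.8 disappears. If the sponsor wants it, keep it as a second run, labelled as observed-case and to be read against 8.2.3.8.

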8.2.4 HiSCR depth

As an additional exploratory analysis of HiSCR, the algorithm applied to derive response at each visit (as described in [Section 8.2.1](#)) will be adapted to evaluate varying depths of HiSCR during

the Treatment Period. A modified HiSCR will be calculated using different criteria for % Δ AN, namely 25%, 75% and 90%, in order to derive a response at each visit. In the summaries of HiSCR depth, the primary efficacy variable will be referred to as HiSCR and the other depth variables referred to as modified (m) mHiSCR25, mHiSCR75 and mHiSCR90.

8.2.5 Presentation of HiSCR

HiSCR will be listed together with the component efficacy data as specified in [Section 8.3.1](#). This listing will include the different HiSCR depth variables (i.e. mHiSCR25, HiSCR, mHiSCR75 and mHiSCR90).

The number and percentage of subjects who achieved HiSCR will be tabulated overall by treatment group and visit, and also by Baseline Hurley Stage and by concomitant antibiotic use at study entry; and also by Baseline Hurley Stage and rescue medication use at any time during the study. This summary will be presented for the PPS and will include the 95% CI for the percentage of subjects with an HiSCR, calculated using a Wilson approximation. The summary will be presented based on NRI and repeated for observed cases. For the observed cases analysis, the denominator for the percentage calculations will be the number of subjects with non-missing HiSCR data in the PPS for each treatment group, visit and Baseline Hurley Stage or concomitant antibiotic use at study entry (as applicable).

The number and percentage of subjects who achieved mHiSCR25, mHiSCR75 and mHiSCR90, together with 95% confidence intervals, will be presented overall and by Baseline Hurley Stage, and by treatment group and visit based on observed cases for the PPS.

All tabulations described in this section will be repeated for the FAS. For the observed cases analysis, the denominator for the percentage calculations will be the number of subjects in the FAS for each treatment group, visit and Baseline Hurley Stage or concomitant antibiotic use at study entry (as applicable) with non-missing HiSCR data. Listings will be presented for the SS.

A figure will be presented showing the percentage of subjects who achieved HiSCR, together with 95% CIs (calculated using a Wilson approximation), over time. All treatment groups will be overlaid on the same plot. The plot will be generated based on NRI and observed cases for the PPS and the FAS. These plots will be repeated for the percentage of subjects who achieved the different HiSCR depths; mHiSCR25, mHiSCR75 and mHiSCR90.

Additionally, for the PPS and FAS, based on NRI and observed cases, the following bar charts will be presented showing the percentage of subjects who achieved HiSCR during the Treatment Period:

- by treatment group and visit
- by treatment group, visit and Baseline Hurley Stage
- by treatment group and Baseline Hurley Stage at Week 12
- by treatment group, Baseline Hurley Stage and concomitant antibiotic use at study entry, at Week 12
- by treatment group, Baseline Hurley Stage and rescue medication use at any time during the study, at Week 12

In addition to the above bar charts, a stacked bar chart displaying whether the criteria are met (yes/no) for each of the component data used in the calculation of HiSCR (% Δ AN, abscess count and draining tunnel [fistula/sinus tract] count) will be generated by treatment group and visit for the PPS and FAS. This graph will summarize the proportion of subjects in each of the 8 different yes/no binary responses at each visit (2 x 2 x 2 response combination) at each visit.

The following bar charts will be presented for the different HiSCR depths based on observed cases for the PPS and FAS:

- by treatment group and visit
- by treatment group, visit and Baseline Hurley Stage

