5.1.2 Study duration per subject

For each subject, the study will last a maximum of 34 weeks. This includes the following study period durations:

- Screening Period: ≥ 2 weeks up to a maximum of 4 weeks, from the time of informed consent up to randomization and administration of IMP at Baseline (Visit 2).
- Treatment Period: Up to 12 weeks, from the administration of IMP at Baseline (Visit 2) to the assessment of the primary efficacy variable at Week 12 (Visit 11).
- SFU Period: Up to 20 weeks, from the last dose of IMP at Week 10 (Visit 10) to the SFU Visit at Week 30 (Visit 12).

The end of the study is defined as the date of the last visit of the last subject in the study.

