3.2.1.2 Study periods

For each subject completing the study, their maximum study duration will be up to 34 weeks and will comprise the following:

- Screening Period: ≥ 2 weeks with a maximum of 4 weeks prior to randomization
- Treatment Period: 12 weeks
- Safety Follow-Up Period: 20 weeks after the last dose of IMP (scheduled at Week 10, 2 weeks prior to the end of the Treatment Period)

The end of the study is defined as the date of the last visit of the last subject in the study.

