5 STUDY POPULATION CHARACTERISTICS

5.1 Subject disposition

The number and percentage of subjects who were randomized into the study, subjects who completed or prematurely discontinued the study, as well as the primary reason for discontinuation will be presented by treatment group and for all subjects, based on the RS. A subject who completed the study is defined as a subject who completed all visits up to the last scheduled study visit, ie, Visit 12 (Week 30).

In addition, the number and percentage of subjects completing Week 4 and Week 12 of the Treatment Period will be presented. A subject is defined as completing Week 4 and Week 12, respectively, if adequate efficacy data are available in the database to calculate the primary efficacy variable at the respective visit.

The number and percentage of subjects who discontinued due to AEs will be summarized separately by treatment group and for all subjects, based on the RS. This will be used for European Union Drug Regulating Authorities Clinical Trials (EudraCT) reporting.

The number and percentage of subjects included in each of the analysis sets will be summarized by treatment group and for all subjects based on the ES. Percentages will be calculated based on the RS for the purpose of this summary.

Screen failure reasons will be summarized for the ES. A listing of subjects who did not meet study eligibility criteria (including a glossary) will also be presented for the ES.

In addition, the following listings will be presented by treatment group:

- Subject disposition (ES)
- Study discontinuation (RS)
- Visit dates (SS)
- Subject analysis sets (ES)

The listing of subject disposition will include the date of informed consent, date of pharmacogenetic informed consent (for subjects participating in the pharmacogenetic substudy), date of randomization, date and time of first and last dose of IMP, date of premature study termination and primary reason (if applicable), and date of final contact. If applicable, the date and reason for premature unblinding will also be included.

The listing of study discontinuation will include the primary reason for discontinuation and the number of days on IMP.

The number of days on IMP will be calculated as follows:

$$\text{Number of days on IMP} = (\text{Date of Last Dose Received} - \text{Date of First Dose Received}) + 1$$

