6.6 Prior and concomitant medications

Prior and concomitant medications (as defined below) will be listed for the RS by treatment group and subject, and summarized for the SS by WHODD Anatomical Main Group (Level 1), Pharmacological Subgroup (Level 3) and PT. The reported term will be included in the listing, together with flags to identify antibiotic and rescue medications, respectively. Separate summaries will be presented for prior medications and concomitant medications and these will be presented by treatment group and for all subjects. Prior medications which continued into the study period are also classified as concomitant and are included in both summaries.

Separate summaries will be presented for the following, identified using WHODD Anatomical Main Group codes, the indication recorded on the eCRF and medical review of the recorded data:

- Prior and concomitant HS medications
- Concomitant antibiotic medications at study entry
- Rescue medication during study

All HS medications, antibiotics and rescue medication given during the study will be identified via medical review of the concomitant medications and confirmed at the DEMs prior to unblinding.

Concomitant antibiotic medication at study entry is defined as any antibiotic with start date on or prior to first dosing, and end date on or after screening.

All tabulations will be sorted alphabetically by Level 1 term, alphabetical Level 3 term within Level 1 and decreasing frequency of PT in the 'All Subjects' column.

The listing will include a flag for prohibited prior and concomitant medications. These will be confirmed and documented at the final DEM.

A glossary of all prior and concomitant medications will be presented for the RS including the Anatomical Main Group (Level 1), Pharmacological Subgroup (Level 3), PT and reported term.

Any medications with partially missing dates will be handled as described in [Section 4.2.4](#) in order to classify them as prior or concomitant.

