8.2.1 Derivation of the primary efficacy variable

The following algorithm will be applied to derive the HiSCR at each visit, based on total lesion counts across anatomical regions for the 3 relevant lesion types recorded as specified above in [Section 8.1](#):

1. Calculate the AN count at each visit as the total number of abscesses plus the total number of inflammatory nodules, across all anatomical regions
2. Calculate the percentage change from Baseline in AN count (%ΔAN) at each visit as

$$100 \times \frac{(AN \text{ count at post-Baseline visit minus Baseline AN count})}{(\text{Baseline AN count})}$$

3. Calculate the change from Baseline in the abscess count by subtracting the Baseline abscess count from the abscess count at each post-Baseline visit
4. Calculate the change from Baseline in the draining tunnel (fistula/sinus tract) count by subtracting the Baseline draining tunnel (fistula/sinus tract) count from the draining tunnel (fistula/sinus tract) count at each post-Baseline visit
5. If the %ΔAN is less than or equal to -50%, and the change from Baseline in the abscess count is zero or negative (ie, non-positive) together with a non-positive change from Baseline in the draining tunnel (fistula/sinus tract) count, then the HiSCR will be assigned a value of 1 (ie, HiSCR is achieved); otherwise, the HiSCR will be assigned a value of 0 (ie, HiSCR is not achieved).

There will not be any imputation of missing lesion count data in the derivation of the HiSCR at any visit. In such cases the HiSCR will be missing and rules for handling missing HiSCR values in the analysis will be applied ([Section 4.2.1](#) and [Section 8.2.3](#)).

The primary efficacy variable is attained if the subject has a HiSCR of 1 at Week 12.

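### Week 12 HiSCR is displayed by rescue use over the whole study, so rescue taken up to about 18 weeks after the endpoint decides which subgroup a subject is in

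*SAP*

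**What the plan says.** SAP Section 8.2.5 lists bar charts of the percentage of subjects achieving HiSCR. One is to be shown "by treatment group, Baseline Hurley Stage and rescue medication use at any time during the study, at Week 12". The tabulation of HiSCR by treatment group and visit, described earlier in that section, is to be given "and also by Baseline Hurley Stage and rescue medication use at any time during the study".

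The endpoint has a fixed time. SAP Section 8.2.1 states: "The primary efficacy variable is attained if the subject has a HiSCR of 1 at Week 12".

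The study lasts well beyond that time. Protocol Section 5.1.2 describes the follow-up period as running "from the last dose of IMP at Week 10 (Visit 10) to the SFU Visit at Week 30 (Visit 12"). SAP Section 3.2.1.2 lists it among the study periods: "Safety Follow-Up Period: 20 weeks after the last dose of IMP". SAP Section 5.1 defines a study completer as someone who "completed all visits up to the last scheduled study visit, ie, Visit 12 (Week 30").

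On the source of the rescue flag, SAP Section 6.6 says: "All HS medications, antibiotics and rescue medication given during the study will be identified via medical review of the concomitant medications". Protocol Table 5-1 and Section 8.10 still collect concomitant medications at the Safety Follow-Up Visit.

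Elsewhere the SAP uses a shorter window. The Bayesian rescue analysis in Section 8.2.3.6 "will treat subjects who receive specific rescue medication prior to the Week 12 visit as non-responders". The general rule in Section 4.2.1 lets rescue count from the time it is taken to the end of the Treatment Period.

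**The concern.** The split conditions a Week 12 result on something that may happen after Week 12. Taken literally, a subject first rescued at Week 25 would be shown in the rescue bar for Week 12 response.

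This is a realistic possibility. Dosing stops at Week 10, Protocol Section 2.1.2 notes that the disease can return quickly once drug is stopped, and Protocol Section 7.8.3 allows rescue for flares during the study.

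A reader of the chart will naturally ask whether subjects who needed rescue responded less well, or whether rescue contributed to response. Rescue after the endpoint answers neither question. It may itself depend on how the subject was doing at Week 12, so it can create a gap between the bars that has nothing to do with rescue before the endpoint. The arms are small (about 40, 20 and 20 subjects) and are divided again by Hurley Stage, so a few such subjects could change the picture.

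**Working it through.** **1. Reproduce the plan's calendar.** The last dose is at Week 10 and follow-up is 20 weeks: 10 + 20 = 30, matching the stated Week 30. Screening of up to 4 weeks gives 4 + 30 = 34, matching the stated maximum of 34 weeks.

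**2. Length of the post-endpoint window.** 30 − 12 = 18 weeks at nominal visit times. With the visit windows in Protocol Section 8 (±3 days at Week 12; −3 to +7 days at Safety Follow-Up):

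- Shortest: (210 − 3) − (84 + 3) = 120 days, or 17.1 weeks.
- Longest, with follow-up counted from nominal Week 30: (210 + 7) − (84 − 3) = 136 days, or 19.4 weeks.
- Longest if the Week 10 dose is also 3 days late: (70 + 3 + 140 + 7) − (84 − 3) = 139 days, or 19.9 weeks.

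These are for subjects who complete dosing. A subject who stops treatment early has follow-up 20 weeks after that last dose, so the gap can be shorter. Limiting the split to rescue before the Week 12 visit brings the post-endpoint window to 0.

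**3. Look for a cut-off elsewhere.** Section 6.6 sets none for rescue. The lead-in to the charts in Section 8.2.5 mentions the Treatment Period, but that phrase qualifies when HiSCR is achieved, not when rescue is used. Where the SAP wants to limit a subject-level flag to the Treatment Period it says so, as in the disease-flare summary in Section 8.3.1.2.

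**4. Can the split create a gap on its own?** The documents give no rescue rates, so the rates here are assumptions. Suppose nobody is rescued before Week 12. Let p be the true Week 12 response rate, and let r_R and r_N be the probabilities of follow-up rescue in Week 12 responders and non-responders. The displayed rates are then:

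- rescue group: p·r_R / [p·r_R + (1 − p)·r_N]
- no-rescue group: p(1 − r_R) / [p(1 − r_R) + (1 − p)(1 − r_N)]

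The sample-size section assumes p = 70% for bimekizumab and 27.6% for placebo.

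| p | r_R | r_N | Rescue group | No-rescue group |
|---|---|---|---|---|
| 70% | 10% | 10% | 70.0% | 70.0% |
| 70% | 10% | 20% | 53.8% | 72.4% |
| 70% | 10% | 40% | 36.8% | 77.8% |
| 70% | 40% | 10% | 90.3% | 60.9% |
| 27.6% | 10% | 10% | 27.6% | 27.6% |
| 27.6% | 10% | 40% | 8.7% | 36.4% |
| 27.6% | 40% | 10% | 60.4% | 20.3% |

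As an example, the fourth row is 0.70 × 0.40 / (0.70 × 0.40 + 0.30 × 0.10) = 0.28 / 0.31 = 90.3%.

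In every row no rescue precedes the endpoint, yet the bars separate whenever r_R and r_N differ. Which bar is higher depends only on whether responders or non-responders are rescued more often in follow-up.

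**The case against.** The strongest reply is that nothing inferential depends on this display. SAP Section 3.1 limits formal testing to the primary variable, the success criterion does not use the split, and the effect of rescue on Week 12 response is handled in Sections 8.2.3.6 and 8.2.3.10. That stands, and it limits the weight of the point.

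A second reply concerns the tabulation. It runs by visit, and one whole-study flag keeps subgroup membership constant across rows. A flag redefined at each visit would make membership and denominators shift. That is a fair trade-off, so no visit-specific flag is required here. It does not rescue the Week 12 chart, which has a single time point.

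There are also stronger readings that a reader might infer but the documents do not support:

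- **That the rescue group's response is inflated**, because responders who relapse off treatment enter it. Non-responders rescued in follow-up enter it too, and the illustration moves either way.
- **That Section 8.2.5 contradicts Section 8.2.3.6.** The latter recodes outcomes, while the former stratifies a display and states its own window. The windows differ, but neither section breaks the other.
- **That 18 of 30 weeks (60%) measures the impact.** It is a share of calendar time, not of rescue use or of misplaced subjects. The documents give no rescue subgroup sizes from which a percentage-point shift could be worked out.

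**Conclusion.** The point holds as a minor one about descriptive outputs. As written, the Week 12 split counts rescue over a window that extends about 18 weeks past the endpoint (17.1 to 19.9 weeks across the visit windows for subjects who complete dosing). A difference between the rescue and no-rescue bars can therefore be an artefact. Its direction and size cannot be determined from the documents, and the percentages in the illustration rest wholly on assumed rescue rates.

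The conclusion rests on reading the study as running to Week 30, which SAP Sections 3.2.1.2 and 5.1 support, and on the absence of any Week 12 cut-off for rescue in Sections 6.6 and 8.2.5.

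There is one practical side effect. At the second interim, follow-up need not be complete for every subject. If this display is produced then (its content is set in a separate interim SAP), subgroup membership could change by the final analysis although no Week 12 response has changed.

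**What to change.** In SAP Section 8.2.5, for the Week 12 bar chart and the Week 12 rows of the tabulation, define the split as rescue medication use before the Week 12 visit, the window already used in Section 8.2.3.6. Label the split as descriptive and post-randomization, because even with the right window rescue use is an outcome of treatment and not a baseline characteristic. If the whole-study flag is kept for other rows of the by-visit table, say so in a footnote.

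The cost is small: no new data and no change to any rescue rule. SAP Section 1 does require an amendment for a changed definition before database lock, and Section 3.9 shows that this SAP version already follows the second unblinded interim. The change should therefore carry a short documented rationale.
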